#### **Co-primary endpoint**

- Change in lumbar spine BMD from baseline to 6 months after the zoledronic acid infusion.
- The proportion of patients who fails to maintain BMD (total hip, femoral neck and spine). Failure is defined as  $\geq 3$  % BMD loss at the lumbar spine or  $\geq 5$  % BMD loss at the femoral neck or total hip.

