### **Statistical analysis and power calculation**

Baseline characteristics of the three groups will be presented using descriptive analysis and compared using ANOVA and post-hoc unpaired t-tests if ANOVA demonstrates differences between the groups. Changes in bone mineral density one year after the zoledronic acid infusion within groups will be investigated using paired-sample t-tests and compared with the changes reported after stopping denosumab after two years [12] for the three groups combined and individually using one-sample t-test. The proportion of patients who fails to maintain BMD will be compared between groups using chi-sq test. Changes in bone mineral density, HRpQCT measures and markers of bone turnover will be compared between groups using mixed model analysis. Exploratory analyses will include multiple regression analyses aiming at identifying baseline factors or changes occurring at three or six months, which affect the change in BMD one year after the zoledronic acid infusion. Factors included in this analysis will be gender, age, years of treatment with denosumab, baseline BMD, baseline bone turnover markers, change in bone turnover markers three and six months after the zoledronic acid infusion.

Based on a previous study a 5% decrease in lumbar spine BMD can be expected during the first year after discontinuation with a 3% standard deviation [12]. The hypothesis is that treatment with zoledronic acid can decrease this bone loss. Eighteen patients will be needed to demonstrate a bone loss  $\geq 2.5$  % using a paired-sample t-test with a power of 90% and level of significance of 5%. If the decrease is less than that BMD is maintained and the hypothesis can be accepted. To account for dropouts n is increased to 20 in each group. As comparisons between the different treatment regiments suggested in this protocol never have been done before, we cannot estimate differences between groups. However, the least significant change in lumbar spine BMD using DXA is 3%. The SD of lumbar spine BMD in our facility is 3% [18]. To be able to demonstrate a difference in change in lumbar spine BMD between the three groups equal to the least significant change using independent samples t-test we need 16 patients in each group with a standard

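### The 2.5% maintenance rule names no visit and no confidence limit; applied to the six-month co-primary, it cannot reliably separate an inactive from an active infusion in the 6-month group

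*Combined protocol and SAP*

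**What the plan says.** The sample-size paragraph under *Statistical analysis and power calculation* assumes that "a 5% decrease in lumbar spine BMD can be expected during the first year after discontinuation", with an SD of 3%. It continues "Eighteen patients will be needed to demonstrate a bone loss" of 2.5% or more, by paired t-test with 90% power at the 5% level, and then gives the decision rule: "If the decrease is less than that BMD is maintained and the hypothesis can be accepted". The rule names no visit, no test of the mean against 2.5% and no confidence limit. The planned group size, with an allowance for dropout, is 20.

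The plan points to two different visits:

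- *Co-primary endpoint* lists "Change in lumbar spine BMD from baseline to 6 months after the zoledronic acid infusion".
- *Duration of study* places the primary endpoints at 12 months after infusion, and the statistical section places the within-group paired t-tests on BMD at one year after infusion.

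Infusion timing is in *Investigations* (Treatment paragraph): day 0 in the 6-month group, month 3 in the 9-month group, and month 6 at the latest in the observation group. Earlier infusion is possible in the last two groups if a trigger is met.

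**The concern.** A bound is useful only if an untreated group would clearly exceed it over the same period. Against a one-year untreated loss of 5%, a bound of 2.5% does that. Against a six-month loss it may not. In the 6-month group, the six-month co-primary covers only six months from baseline, and an untreated group could by then have lost roughly 2.5%, or less. A result under the bound would then say little about the drug, yet the wording would let the hypothesis be accepted.

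This matters more because the trial has no untreated control; *Safety and ethical considerations* calls it uncontrolled. The claim that bone loss was prevented therefore leans on external benchmarks. The missing confidence limit adds to the problem, since the rule can be read as a comparison of the observed mean with 2.5%, or as acceptance when a test fails to show a loss.

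**Working it through.** **Inputs.** Untreated loss 5% in the first year, SD 3%, bound 2.5%, 18 needed and 20 planned per group: all from *Statistical analysis and power calculation*. Infusion times: *Investigations*. Scan months: the study-plan tables under *Duration of study*.

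**1. The plan's own figure.** For a two-sided paired t-test with a difference of 2.5, SD 3 and alpha 0.05, the noncentral t gives 89.7% power at n=17 and 91.5% at n=18. The smallest n reaching 90% is 18, as stated. The sample size is not in question.

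**2. Time from baseline to the six-month co-primary.** 0+6 = 6 months (6-month group), 3+6 = 9 months (9-month group), and up to 6+6 = 12 months (observation group).

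**3. Untreated loss over those intervals.** The documents give only the one-year total. If loss were even (an assumption), 5% × 6/12 = 2.5%, 5% × 9/12 = 3.75%, and up to 5%. Only the 6-month group then sits at the bound.

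**4. Chance that an inactive infusion passes, n=20.** The standard error is 3/√20 = 0.671. For a true mean loss L:

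- Reading A, observed mean loss below 2.5%: Φ((2.5 − L)/0.671).
- Reading B, paired t-test against zero shows no significant loss: noncentral t, 19 degrees of freedom, noncentrality L/0.671. An observed loss of up to 1.40% is non-significant if the sample SD is 3%.
- Reading C, upper 95% confidence limit of the mean loss below 2.5%: noncentral t, noncentrality (2.5 − L)/0.671.

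| True loss L | A | B | C |
|---|---|---|---|
| 1.5% | 93% | 44% | 29% |
| 2.0% | 77% | 19% | 11% |
| 2.5% | 50% | 5.8% | 2.5% |
| 3.0% | 23% | 1.1% | 0.4% |
| 3.5% | 7% | 0.1% | 0.04% |
| 5.0% | 0.01% | <0.01% | <0.01% |

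The 50% in reading A does not depend on n, because the true loss then equals the bound. For the 9-month group at an even-loss 3.75%, reading A gives Φ(−1.25/0.671) = 3.1%.

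**5. Same check at twelve months in the 6-month group.** With L = 5%, the last row applies: 0.01% or less on every reading.

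**6. What a confidence limit does alone.** Reading C removes the ambiguity of A and B, but it does not repair a six-month read if the untreated loss is under 2.5%: an inactive infusion still passes 11% of the time at 2.0% and 29% at 1.5%. The visit has to be fixed as well.

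**The case against.** The strongest reply is that the plan already works on a one-year scale. The sentence before the rule refers to a paired t-test, the only paired t-tests on BMD in the plan are at one year, and *Duration of study* puts the primary endpoints at 12 months. No sentence applies 2.5% to the six-month change. This largely stands: on that reading the problem almost disappears. What it leaves is that the endpoint definition itself says six months and the rule is attached to neither visit.

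Several stronger readings are tempting, but the documents do not support them:

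- *An inactive infusion passes half the time.* This needs both even loss and the observed-mean reading. It is also unclear whether the first year off drug starts at the last injection or when the effect ends. If at the injection, more of the 5% could fall in this group's six-month window and the pass rate drops. The remark under *Aims* that some patients are still suppressed at six months points the other way.
- *2.5% is the plan's only efficacy bound.* *Co-primary endpoint* defines failure as a loss of at least 3% at the spine or 5% at the hip sites, and a one-sample t-test compares one-year changes with published off-treatment changes.
- *The rule would create a false timing effect.* Groups are compared by mixed model and chi-square test, not by which of them falls under 2.5%.
- *2.5% was chosen as half of the untreated loss.* That is arithmetic; the plan gives no reason for the figure.

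**Conclusion.** The point holds as a gap in the decision rule. The 2.5% bound makes sense beside a one-year loss of 5%, but the plan leaves it open to use on a six-month co-primary for which it gives no untreated loss. If used there in the 6-month group, an inactive infusion would pass on the observed mean in 93% to 7% of trials for assumed six-month losses of 1.5% to 3.5% (50% if loss is even). If a non-significant t-test decides, it would pass in 19% at 2.0% and 5.8% at 2.5%. These figures assume n=20, SD 3% at six months as at one year, and normally distributed changes. The width of the range is itself the finding: the documents cannot say how well the rule discriminates at six months. At a 5% loss either reading passes 0.01% or less.

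**What to change.** 1. Reconcile the primary time point across *Co-primary endpoint*, *Duration of study* and *Statistical analysis and power calculation*.
2. State that the 2.5% rule applies to the change from baseline to one year after infusion. That is the visit of the planned paired t-test, and every group has a scan then (M12, M15, Mx+12).
3. Declare maintenance only if the upper 95% confidence limit of the mean loss is below 2.5%.
4. Report the six-month co-primary as an estimate with confidence interval and as the between-group comparison, and state that it cannot by itself support a maintenance claim.

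Two alternatives are weaker. Fixing the rule at twelve months from baseline leaves the 9-month group without a scan (it has M9 and M15). Scaling the bound to 1.25% for six months rests on the even-loss assumption, has 42% power at n=20 under the confidence-limit rule if the true loss is zero, and would need 63 per group for the plan's own 90%-power paired t-test.

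The change is to wording only, with no new visits or patients. The maintenance conclusion waits for the one-year scan. At n=20 and SD 3% the confidence-limit rule has 94% power if the true loss is zero but about 56% if it is 1%. One year after infusion is still 12, 15 and up to 18 months from baseline in the three groups, so the report should state those intervals beside each result.

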### **Randomization**

The patients will be randomized to infusion of zoledronic acid administered either six (6-month-group, n=20) or nine months (9-month group, n=20) after the last denosumab injection or to observation in the form of monthly monitoring of bone resorption (observation group, n=20). If p-CTX increases above 1.26 ug/l in patients in the observation group or the nine months group, zoledronic acid will be administered. If BMD decreases by more than 5% at any site after three months in the observation group, infusion of zoledronic acid will be administered.

The randomization code will be generated by the hospital pharmacy, Aarhus University Hospital. Participants will be randomized in blocks of 6.

---

 In case of dropouts the randomization codes will be reused. The codes will be randomized amongst the new participants.

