deviation of 3%, power of 80% and significance level of 5%. Thus, the already planned 20 participants per group are sufficient to make meaningful exploratory analyses. New participants will be enrolled after four dropouts in total. Per-protocol analysis will be performed.

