### **Termination of the study**

The study will be stopped if new information about serious or life-threatening side effects occurring at a frequency that may cause general concern about the safety of zoledronic acid comes to the investigator's knowledge. The study will be terminated for single participants if the investigator suspects that the participant will be in risk of serious, life-threatening events if she continues as part of the study.

The patients will be referred to the outpatient clinic at Aarhus University Hospital after termination of the study.

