### **Research plan and facilities**

November 2016-October 2017: Recruitment of participants

November 2016-April 2020: Clinical trial on-going

May 2020-October 2020: Analysis and publication

We have all the facilities for the clinical study including DXA- and HRpQCT-scanners. We have experienced research nurses and laboratory technicians and we have access to analyses of biochemical markers at our Department of Clinical Biochemistry.

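### The only analysis set named is an undefined per-protocol set and dropouts are replaced, so no stated analysis keeps all randomised patients or would reveal attrition bias

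*Combined protocol and SAP*

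**What the plan says.** All references are to the combined protocol and SAP.

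- **Analysis population.** The section Statistical analysis and power calculation ends with "Per-protocol analysis will be performed". Nothing says which patients qualify, and no intention-to-treat or full analysis set appears anywhere.
- **Replacement.** The same section states "New participants will be enrolled after four dropouts in total". Footnote 4 under Randomization adds "In case of dropouts the randomization codes will be reused. The codes will be randomized amongst the new participants".
- **Tests.** For the failure co-primary: "The proportion of patients who fails to maintain BMD will be compared between groups using chi-sq test". Within-group BMD change is tested by paired and one-sample t-tests, and between-group change by a mixed model. None of these names its own population.
- **Within-group criterion.** After sizing the trial to detect a 2.5% loss, the plan says "If the decrease is less than that BMD is maintained and the hypothesis can be accepted".
- **Dropout allowance.** "To account for dropouts n is increased to 20 in each group", up from 18.
- **Missing values.** The only rule of this kind is in Investigations and covers blood results outside the detection range. There is none for BMD.
- **Individual termination.** "The study will be terminated for single participants if the investigator suspects that the participant will be in risk of serious, life-threatening events" is the one stated rule.

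**The concern.** The chi-square test and the t-tests need an observed outcome from each patient. A patient who leaves without a follow-up DXA therefore falls out of them by default, and under the replacement rule may be substituted by someone else. Only the mixed model could use the scans of a patient who left early, and the text does not say that it will.

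The within-group criterion is a threshold on mean loss, and a result below it counts as success. If the patients who leave are those losing more bone, the remaining sample looks better than the randomised one and success is easier to declare. Because no analysis of all randomised patients is planned, there would be nothing to compare against.

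The missing definition matters more here than in most trials, because treatment can be triggered by the outcome. Under Design, Randomization and Investigations, the 9-month and observation groups can be infused early on raised p-CTX or a clinical fracture. The observation group can also be infused early on BMD loss, and re-infusion is possible in any group. The plan does not say whether such patients are per-protocol. An analyst who excluded them would be selecting on the outcome. Before first infusion that selection would also differ by arm, since the 6-month group is infused at day 0.

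**Working it through.** **1. The plan's own figures.** The inputs are in Statistical analysis and power calculation; two-sided tests are assumed, since sidedness is not stated.

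- Paired t-test with d = 2.5/3 = 0.833, 5% level, 90% power: n = 17.17, so 18, as stated.
- 18/(1 − 0.10) = 20, as stated. The allowance is 2 per arm, or 2 × 3 = 6 overall.
- Between groups, difference 3, SD 3, 80% power: 16 per group by the normal approximation, as stated (16.7, so 17, by exact t).

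The sample sizes are not in dispute. Dropout is provided for twice: by the step from 18 to 20, and by replacement once 4/60 = 6.7% have left.

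**2. Shift in mean loss.** The documents supply N = 60, SD = 3% and k = 4 dropouts (the replacement trigger). The assumptions are that dropouts leave the analysis, and that dropout propensity has correlation ρ with bone loss, higher losers leaving. Simulation of 200,000 trials gives 0.403 percentage points at ρ = 1 (the four worst losers leave).

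As a check, shift = k × m × SD × ρ/(N − k), where m is the mean standardised loss of the four worst. Solving, m = 0.403 × 56/(4 × 3) = 1.88. The shift is proportional to ρ: 0.3 × 0.403 = 0.121 and 0.5 × 0.403 = 0.202.

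| Dropouts | ρ = 0 | ρ = 0.3 | ρ = 0.5 | ρ = 1 | ρ = 1, all refilled |
|---|---|---|---|---|---|
| 4 | 0 | 0.12 | 0.20 | 0.40 | 0.38 |
| 6 | 0 | 0.17 | 0.29 | 0.57 | 0.51 |

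For four dropouts at ρ = 0.3 to 0.5 this is 0.12/2.5 = 5% to 0.20/2.5 = 8% of the 2.5-point criterion. It is also 0.18 to 0.30 of one arm's standard error, 3/√20 = 0.67. With negative ρ the signs reverse.

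**3. Shift in the failure proportion.** This uses the lumbar spine only, one of three sites in the composite, with failure at a loss of 3% or more and four dropouts.

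- True mean loss 2.5% (assumed): P = 1 − Φ((3 − 2.5)/3) = 43.4%. After dropout it is 41.7% at ρ = 0.3 and 40.7% at ρ = 0.5. At worst it is (0.434 × 60 − 4)/56 = 39.3%, or 39.6% if all four are refilled.
- True mean loss 1% (assumed): P = 1 − Φ(2/3) = 25.2%; at worst 19.9%.

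**4. Extreme bound in one arm.** If one arm of 20 loses its four worst losers, its mean shifts by 1.0 point (0.8 refilled). Four random dropouts all fall in one arm with probability 3 × C(20,4)/C(60,4) = 3 × 4,845/487,635 = 3.0%.

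**5. Counting missing as failure.** Assume 17 failures among 56 completers: 17/56 = 30.4%. With four dropouts counted as failures, (17 + 4)/60 = 35.0%, a rise of 4.6 points. The worst-case distortion in step 3 at a mean loss of 2.5% was 43.4 − 39.3 = 4.1 points, so this device can overcorrect.

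**The case against.** A reader might infer that both co-primaries are biased towards maintained BMD. The documents do not support that. It requires that patients losing more bone leave; if those losing less leave, the bias reverses. The plan gives no reasons for dropout by arm. The individual termination rule rests on judged risk, which may or may not follow bone loss. The triggers for early and repeat infusion allow some worsening patients to be treated within the trial rather than withdrawn, though how many is not stated.

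The between-group comparison of BMD change is also less exposed. A mixed model can use partial data, and attrition that is similar across arms largely cancels in a between-arm contrast. The trial is open label, so dropout could differ by arm, but nothing in the documents shows that it would. No between-arm bias is computed above.

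A reader might also infer that replacement breaks the randomisation. It does not: the reused codes are themselves randomised among the new participants. What is lost is the patients who left. The first four may not be replaced at all, so the refilled figures are approximate.

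Finally, the illustration measures attrition, not exclusion for protocol deviation. Treatment is normally one supervised infusion, so adherence exclusions may be few.

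All of this stands and limits the size of the problem. It does not supply the missing all-randomised analysis.

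**Conclusion.** The omission is certain: per-protocol is the only set named, it is undefined, dropouts are replaced, and no rule covers missing BMD. Followed as written, the plan can discard randomised patients without any analysis that would show the effect.

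Whether this causes bias, and in which direction, is unknown. The exposed quantities are the within-group 2.5% criterion and the failure proportion. On the stated SD, with four dropouts and a moderate assumed correlation, the effect is small: up to 0.20 points on mean loss and 1.7 to 2.7 points on the lumbar spine failure proportion. The larger figures need the worst losers to be exactly those who leave. This is a cheap improvement, not a flaw that invalidates the design.

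**What to change.** Amend the statistical section as follows.

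1. **Primary set.** Analyse all randomised patients in their assigned arm, including randomised replacements, with every available DXA in the planned mixed model. Keep the data of patients who left alongside those of their replacements.
2. **The 2.5% criterion.** Take each arm's within-group change and confidence interval from that model in place of the paired t-test on completers.
3. **Leaving before infusion.** The co-primary change is timed from the infusion, so a 9-month or observation patient who leaves first has no endpoint date. State how such patients enter, for example with time counted from baseline, or as missing in the sensitivity analysis.
4. **Sensitivity analyses.** Count missing outcomes as failures, labelled as a pessimistic bound that may overcorrect. Separately, exclude the replacements.
5. **Per-protocol.** Keep it as supportive and define it, stating that infusions given under the protocol's own triggers are not deviations.

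The cost is SAP wording and a little more analysis work. It needs no new patients, visits or scans: no DXA after withdrawal is planned, so the analysis uses scans already collected. It can be settled before the analysis period given as "May 2020-October 2020: Analysis and publication". The downside is that results may be less precise or less favourable.

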### **Recruitment of participants**

The patients will be recruited from the outpatient clinics and the DXA units to which patients are referred from their general practitioner at:

Department of Endocrinology and Internal Medicine  
Aarhus University Hospital

Possible participants will be approached during visits or by letter. Patients with osteoporosis living in the Central Region of Denmark, who have redeemed five or six prescriptions for denosumab in the last three years, will be approached by letter. All staff at the outpatient clinics will be informed about the study including inclusion and exclusion criteria. If the patient is interested in receiving further information, he or she will receive written information about the project. Moreover, we will advertise in daily newspapers and on the webpages [www.forsogsperson.dk](http://www.forsogsperson.dk) and [www.sundhed.dk](http://www.sundhed.dk). Participants who respond to advertisements will be sent written information. Subsequently, all possible participants will be invited to a meeting to obtain oral information from one of the investigators. Family members or friends are welcome to participate in the meeting as well. Afterwards the possible participant will be given 14 days to consider whether they wish to participate in the study or not, before they sign the consent form. The participants will not take part in the study before the consent form has been signed.

### **Biobanks**

A research biobank will be made during the study. 20 ml of blood (ten glasses of two ml each) will be sampled. The blood samples will be analyzed in batches for changes in bone markers. After the trial has ended, the remaining blood samples will be transferred to another biobank at Aarhus University Hospital and stored for a maximum of ten years before destruction. Participants will be made aware that the biobank is of relation to future research and that blood samples can be destroyed at all times on request of the patient. The participants will be asked to sign a separate consent form before the remaining blood samples are transferred to the research biobanks.

